We were able to develop basic techniques and measurement from 10 patients in each group as initially proposed in the previous version of this protocol. We now propose to increase our enrollment from 30 to 50 subjects in each group based on the recruitment and enrollment data of about 30% of screen failures (33 subjects screen failed out of 108 total). In addition, there have been subjects who have not been able to produce sputum or provide adequate number of sputum cells for analysis (38 subjects out of 65 accrued gave adequate sputum samples). This represents about 60% success rate for sample quality. Therefore, we will need to increase our enrollment numbers to achieve an n=30 per group.

Power Analysis: Based on a similar rate of screen failures and inadequate samples, the analysis is now based on 50 patients in each group. Our group sample sizes of 50 and 50 achieve 90% power to detect a difference of 0.73 given the null hypothesis that the two-group difference is 0 and the estimated group standard deviations are 1.0 and 1.0, with a significance level (alpha) of 0.05 using a two-sided two sample t-test. We will work with [name], our biostatistician for our statistical analysis.

For ENO and EBC analyses, we will express data as means \pm SD for normally distributed variables. For variables that are not normally distributed we will use medians and the interquartile range. We will use statistical analysis including unpaired *t* tests, Kruskal-Wallis test, and regression coefficients as appropriate. P values of < 0.05 will be considered significant. Differential expression of miRNA and hierarchical clustering will be performed with the genomics core. Statistics using *t* tests or algorithms designed specifically for data mining and biochip interpretation will be used. Pathway analyses will also be performed by the genomics computational core.

Anticipated results and alternative approaches

We will continue to recruit patients with WTC exposure or with asthma based on our experience in our asthma registry or our WTC clinic, in which most people are willing and anxious to participate in any study that might help characterize their symptoms.

We plan to also submit an advertisement to the IRB for approval and to use research match (researchmatch.org) a national registry which is a secure, web-based approach as a recruitment method, and will post the advertisement.

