1. Number of Subjects: 90 (this includes the total number of subjects enrolled in phase I and II of the study that are able to produce sputum)

[Number of subjects in Phase II: 40]

The estimated number of subjects to be enrolled (signed consent, including screen failures) is 300.
2. Gender of Subjects: Men and Women (50 % each)
3. Age of Subjects: 18-80 years of age
4. Racial and Ethnic Origin: The sample population of approximately 80 participants is expected to include a distribution of subjects by race/ethnicity in relation to our local population which includes a high percentage of minority subjects (36% White, 35% Black, 50% Hispanic)
5. Inclusion Criteria:

Inclusion for the WTC population with Irritant-Induced Asthma (IA):

Patients will be recruited from the WTC EHC and will have WTC dust cloud exposure, new symptoms after 9/11, and symptoms of wheeze and shortness of breath (> 2x / week) in the 4 weeks before inclusion (persistent symptoms). We will be recruiting new subjects for phase II of the study but participants who will have completed Phase I of the study and were able to produce adequate sputum samples may also be contacted for Phase II.

Inclusion for Allergic Asthma population(AA): Patients will be recruited from the NYUBAR or advertisement and will have asthma as defined by NIH guidelines, persistent symptoms, absence of WTC dust exposure. Participants who will have completed the Phase I of the study and were able to produce adequate sputum samples may also be contacted for Phase II.

Inclusion of Control Population: Patients will be recruited from the NYUBAR and will have no respiratory symptoms, no asthma diagnosis, no WTC dust exposure, no current tobacco use, ≤ 5 p-y history of tobacco use, and normal spirometry with no bronchodilator response and negative methacholine challenge in past 6 months.

Additional inclusion criteria for individuals with IA and AA: ≥ 18 years of age, current nonsmoker, ≤ 5 pack year (p-y) history of tobacco use, spirometry in the past 6 months or on day of evaluation with a bronchodilator response of $\geq 12\%$ and 200 ml improvement in FEV₁ or a positive methacholine challenge test (decrease in FEV₁ $\geq 20\%$ (PC20) after inhalation of ≤ 16 mg/ml of methacholine), inhaled corticosteroid use in previous 1 month or more will be allowed.

Inclusion criteria for Phase II

Successfully completed Phase I

Has asthma according to Phase I diagnostic criteria

Signed consent to be re-contacted

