We will start with 10 patients in each group to develop the basic techniques and measurements. Our group sample sizes of 10 and 10 achieve 80% power to detect a difference of 1.3 given the null hypothesis that the two-group difference is 0 and the estimated group standard deviations are 1.0 and 1.0, with a significance level (alpha) of 0.05 using a two- sided two-sample t-test. Based on results from these studies we will work with [name], our biostatistician and the NYU CI Genomics core for our statistical analysis. We put in a small number of patients as this is a pilot study to develop information that will allow for a subsequent appropriate power analysis.

For ENO and EBC analyses, we will express data as means \pm SD for normally distributed variables. For variables that are not normally distributed we will use medians and the interquartile range. We will use statistical analysis including unpaired *t* tests, Kruskal-Wallis test, and regression coefficients as appropriate. P values of < 0.05 will be considered significant. Differential expression of miRNA and hierarchical clustering will be performed with the genomics core. Statistics using *t* tests or algorithms designed specifically for data mining and biochip interpretation will be used. Pathway analyses will also be performed by the genomics computational core.

For Phase II, the primary outcome is the change in TSLP gene expression in epithelial cells after 2 weeks of treatment of inhaled corticosteroid compared to no treatment. We hypothesize that a significant reduction in the gene expression will be observed in the treatment group of inhaled corticosteroid compared with the untreated group. The difference between two randomized groups will be compared using the two-group *t*-test if data are normally distributed, and the nonparametric Wilcoxon test will be used for skewed data. The effect of inhaled corticosteroids on newly identified epithelial targets (gene expression array) will also be examined. This is an exploratory goal and will be performed after cell stabilization and short-term culture cells to insure appropriate RNA quality.

Sample size and power: Group sample sizes of 15 and 15 achieve 80% power to detect a difference of 1.3SD against the null hypothesis that both group means are equal with a significance level (alpha) of 0.01 using a two-sided two-sample *t*-test assuming equal variance.

3: Data Storage and Confidentiality:

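### Phase I carries two conflicting size and power statements, and the current one takes its power at the 50 accrued per group, not at the roughly 30 who can be analysed for sputum endpoints

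*Combined protocol and SAP*

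**What the plan says.** Phase I size appears in three places in the combined protocol and SAP.

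- **Section III.2, Data Analysis and Data Monitoring**, in the future tense: "We will start with 10 patients in each group to develop the basic techniques and measurements". It then gives the power: "Our group sample sizes of 10 and 10 achieve 80% power to detect a difference of 1.3 given the null hypothesis", "with a significance level (alpha) of 0.05 using a two- sided two-sample t-test". It mentions neither 50 per group nor 0.73.
- **Statistical Analysis** (end of Research Design and Methods) treats that stage as completed: "We were able to develop basic techniques and measurement from 10 patients in each group as initially proposed in the previous version". Enrolment rises from 30 to 50 per group, citing two losses: "about 30% of screen failures (33 subjects screen failed out of 108 total") and inadequate sputum ("38 subjects out of 65 accrued gave adequate sputum samples", rounded to 60% success). The aim is 30 per group. Power is given as 90% for a difference of 0.73 with 50 and 50, SD 1.0, two-sided alpha 0.05, two-sample t-test.
- **Section II, item 1** counts 90 subjects able to produce sputum over both phases, and adds: "The estimated number of subjects to be enrolled (signed consent, including screen failures) is 300". The consent section, item 3, repeats 90 as the number in the data analysis.

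Under Specific Aim 1 (SA1.a), people whose sputum yields too few cells are excluded from data analysis.

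**The concern.** Section III.2 is operative text, not an amendment log, so a reader meets two Phase I designs for the same kind of comparison, at the same alpha and SD, with detectable differences of 1.3 and 0.73. An analyst following one section would report different design assumptions from an analyst following the other.

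The current statement has its own problem. It computes power at the number accrued, although the same section raises accrual precisely because only about 60% of those people give usable sputum. The sputum cell counts and the epithelial RNA work rest on the smaller number. The protocol says that if irritant and allergic asthma do not differ on exhaled markers, it will ask whether the study was powered for a small difference. Any such question, for exhaled or sputum markers, needs a correct power statement at the number analysed.

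**Working it through.** **Inputs.** Difference 1.3 with 10 per group (III.2); difference 0.73 with 50 per group (Statistical Analysis); SD 1.0, two-sided alpha 0.05 and two-sample t-test (both). Adequate sputum 38/65 = 0.585; screen failure 33/108 = 0.306, so 75/108 = 0.694 pass (Statistical Analysis). Target 30 per group, 90 in total; 300 consents (Section II).

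**Formula.** Power from the noncentral t, with df = 2n − 2 and noncentrality = difference × √(n/2).

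**1. The plan's own figures.**
- 10 per group at 1.3: noncentrality 1.3 × √5 = 2.907, df 18, power 78.5% (normal approximation 82.8%). The stated 80% is reproduced to within 2 points.
- 50 per group at 0.73: noncentrality 0.73 × √25 = 3.65, df 98, power 95.1% (normal approximation 95.4%). The stated 90% is not reproduced.

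**2. What the 50 covers.** 30/0.60 = 50, and 50 × 38/65 = 29.2. With the exact rate, 30/(38/65) = 51.3, so 52. Sputum loss alone uses up the step from 30 to 50. If the 50 also had to absorb screen failures, the yield would be 50 × 0.694 × 0.585 = 20.3 per group, which misses the stated aim. The 50 is therefore coherent only as a count after screening.

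**3. Power at the analysable number (difference 0.73 SD).**

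| n per group | Power |
|---|---|
| 10 | 34.0% |
| 30 | 79.4% |
| 40 | 89.7% |
| 41 | 90.4% |
| 50 | 95.1% |

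For 90% power the detectable difference is about 0.85 SD at 30 per group and about 0.65 SD at 50.

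**4. The consent total.**
- Expected need for 90 analysable, two-step rates: 90/(0.694 × 0.585) = 221.7, so 222.
- Expected need on the direct yield of 38/108: 255.8, so 256. The yields differ because 108 − 33 = 75, but only 65 are called accrued; the text does not account for the other 10.
- These counts give 90 only on average, over all groups together. Assume equal consents per group, independent binomial yield and the same rate in each group. The chance that all three groups reach 30 is then:

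| Consents | Two-step yield (0.406) | Direct yield (0.352) |
|---|---|---|
| 222 | 16% | 1% |
| 300 | 97% | 69% |

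**The case against.** **On power.** At 50 per group the true power exceeds 90%, so the claim could be read as conservative. That helps only endpoints measured in all 50; at 30 the claim is too high. A second defence is that the first planned comparison pools both asthma groups against controls. With 60 against 30 the noncentrality is 0.73 × √(60 × 30/90) = 3.265, the same as for 40 per group, and power is about 90%. But the plan states 50 and 50, not 60 and 30, and the subsequent comparison of irritant with allergic asthma is 30 against 30. The pooled comparison does not rescue the statement as written.

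**On Section III.2.** The 10-per-group text is plainly left over from a previous version, and the Statistical Analysis section makes clear which statement is current. That limits the harm, but the text still stands in the section headed Data Analysis.

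**On the 300.** A reader might infer that 300 consents is an error, because it exceeds the expected need by 44 (300 − 256) to 78 (300 − 222). The documents do not support this. The 300 is an estimate of consents and the 90 a count of sputum producers, so they belong to different stages. The gap also depends on the reading. The plan's rounded rates give 90/(0.70 × 0.60) = 214.3, so 215 and a surplus of 85. If 150 had to be analysable, the need would be 370 to 427, and 300 would be 70 to 127 too few. Section II also speaks of recruiting new irritant-asthma subjects for Phase II, while III.1 restricts Phase II to Phase I completers, so the Phase II call on the 300 is unsettled. A margin above the expected need is justified by the probabilities above.

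**On closing early.** A reader might also infer that groups would close with about 20 analysable. That needs a stop at 50 consented per group, which no section states; the stated aim is 30.

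**Conclusion.** The point holds in two parts. First, the current text has two incompatible Phase I size and power statements, and the one in III.2 is superseded. Second, the statement that replaced it does not reproduce: for 0.73 SD, power is 95.1% at the 50 accrued and 79.4% at the 30 analysable, against a stated 90%. For the sputum endpoints the stated power is about 11 points too high (90 − 79.4 = 10.6), or equivalently the difference detectable with 90% power is about 0.85 SD and not 0.73.

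This rests on the plan's own SD, alpha and test, on a single pairwise comparison, and on the sputum rate staying near 38/65. The 300 consents is not an error; what is missing is its derivation.

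**What to change.** 1. In III.2, delete the 10-per-group size and power sentences or label them as the completed pilot stage.
2. Use one statement in Statistical Analysis, Section II and III.2: about 50 to 52 accrued per group after screening, 30 analysable per group for sputum endpoints, and power restated at 30 (about 79% at 0.73 SD, or 90% at about 0.85 SD). Give 95% at 0.73 SD only for endpoints available in all 50. SA1.a does not limit its exclusion to sputum endpoints, so say whether people without adequate sputum stay in the ENO and EBC analyses.
3. In Statistical Analysis, correct the wording that the rise to 50 also covers screen failures. That loss belongs in the consent total: 150/0.694 = 216 consents for 150 accrued.
4. Keep 300 as the estimated consent total and show its derivation: an expected need of 222 to 256 for 90 analysable, plus a margin so that each group reaches 30. Do not lower it to 222. State the Phase II contribution, and account for the 10 people between 75 and 65.

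The cost is protocol wording only. No participants or procedures are added.

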Specific Aim 1: To test the hypothesis that irritant-induced asthma is characterized by elevated markers of inflammation in a manner similar to that described for allergic asthma.

SA1.a We will identify and phenotype individuals with WTC dust cloud-exposed irritant-induced asthma (IA), individuals with allergic asthma (AA) and healthy unexposed individuals (Controls).

SA1.b We will measure biomarkers of inflammation using noninvasive techniques for exhaled nitric oxide (ENO) and 8-isoprostanate from exhaled breath condensate (EBC) in WTC irritant-induced asthma (IA), individuals with allergic asthma (AA) and in healthy unexposed individuals (Controls).

SA1.c We will measure inflammatory cells in induced sputum from individuals with IA, AA and Controls.

Specific Aim 2: To test the hypothesis that the miRNA expression in airway epithelial cells will differ between IA, AA and Control individuals.

SA2.a. We will isolate RNA from epithelial cells and inflammatory cells in induced sputum and assess the miRNA expression profile using microarray technology among individuals with irritant-induced asthma (IA), individuals with allergic asthma (AA) and healthy unexposed individuals (Controls).

SA2.b. We will identify the mRNA targets of the differentially expressed miRNAs by using publicly available databases and correlate miRNA and mRNA expression.

Specific Aim 3: To test the hypothesis that levels of RNA of targets in human sputum cells will differ before and after the administration of inhaled corticosteroids in asthmatics (both IA, AA). The importance of this hypothesis in the characterization of irritant induced and allergic asthma is to further characterize the regulatory pathways expressed in sputum cells by identifying which inflammatory markers are steroid sensitive and steroid resistant.

SA3.a. We will isolate RNA targets in discrete sputum cells from induced sputum in IA and AA individuals and compare levels before and after administration of inhaled corticosteroids.

I. Background and Significance

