We have chosen to use individuals with WTC dust cloud exposure as our model of initial high dose exposure to enhance our ability to identify patients with irritant asthma. We suspect that other more prolonged exposures also induce irritant asthma, but our previous studies and those of other investigators suggest that this exposure provides the highest risk.

We have proposed a positive selection strategy for isolation of bronchial epithelial cells from IS. The possibility exists that this technique may provide too low a yield of cells. Should that be the case, we can use a negative selection strategy using anti-CD14 and anti-CD16 antibody beads to specifically deplete macrophages and neutrophils respectively (37). We may also need to obtain duplicate sputum samples from patients, i.e. have patients return for a second sputum induction.

Our initial analyses will be between our healthy controls and asthma in general (AI and AA) and subsequently between each type of asthma (AI and AA) to optimize our ability to detect differences in sputum markers and miRNA. The

possibility exists that we will find no difference between measurements of markers of inflammation in exhaled breath between AI and AA. Should that be the case, we will have to examine whether our pilot study was powered to identify a small difference.

We are basing our miRNA and mRNA studies on those that have been performed in epithelial cells derived from cigarette smokers (45). These studies have shown a correlation between mRNA and miRNA expression and thus there is precedent for our studies. Because of the high price of each of these chips, and the cost of core analysis time, we initially propose to use 5 subjects for each condition to obtain a global pattern scale. These studies will subsequently be extended to get a reasonable statistical power.

From our pilot studies and recent publication we will continue to investigate mechanisms of asthma and irritant-induced asthma. The studies are high risk but have potential for high yield, and will provide data for subsequent NIH applications for replication and further evaluation for a junior faculty member. In addition, they have potential to provide information that could help target specific interventions for asthma of different phenotypes as we proposed in phase II of the study. As such, they fit the mandate of the CTSI grants.

II. Characteristics of the Research Population

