We will obtain epithelial cells from the lining of the nose using a technique called nasal brushing. This is a simple, nonsurgical procedure and is well tolerated by most people. We will gently brush the inside of the lateral wall of each nostril with a small, delicate, sterile brush. This procedure takes about 5 seconds for each nostril.

We also propose to correlate patterns of miRNA changes in our defined populations, with mRNA expression arrays. HMW RNA from isolated epithelial cells will be used for hybridization to Affymetrix HG-U133 Plus 2.0 microarrays. Images will be analyzed in the core facility and data will be normalized as follows: (1) per array, by dividing the raw data by the 50th percentile of all measurements; and (2) per gene, by dividing the raw data by the median expression level for all the genes across all arrays in a data set. We will determine whether up or down-regulated mRNAs are potential targets for previously identified miRNAs.

Phase II

Only subjects with Irritant asthma or Allergic asthma who have successfully completed the first phase of the study and have signed consent to be re-contacted will be recruited for the second phase of the study (Phase II). Phase II will involve two visits over a 2 week time period. For Phase II, we will first obtain sputum samples for a baseline analysis of cells. Study subjects will be provided with an inhaled corticosteroid, Fluticasone propionate HFA 220 mcg, 2 puffs twice a day (Treatment), or no treatment (No treatment). Fluticasone HFA will be provided by the study physician through the CTSI and the Bellevue Pharmacy. Treatment cases will be instructed to self administer the medication with a large volume spacer that will be provided to them. Inhaler teaching will be performed by study physician or coordinator at the time that the subject is provided the inhaler. Treatment Cases and No treatment controls will be provided a diary to record fluticasone inhaler. Treatment cases and No treatment controls will be allowed to use their usual rescue bronchodilator (albuterol) on an as needed basis. Treatment Cases and No treatment controls will return after 2 weeks for a repeat sputum induction.

2. Data Analysis and Data Monitoring:

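### Phase II pools irritant and allergic asthma with no stratification, phenotype term or by-phenotype steroid effect, so the planned test is silent on the phenotype purpose given for it

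*Combined protocol and SAP*

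**What the plan says.** **Population.** The Phase II text in section III.1 recruits both phenotypes into one study: "Only subjects with Irritant asthma or Allergic asthma who have successfully completed the first phase of the study". Participants receive inhaled corticosteroid or no treatment, and phenotype is not mentioned in the assignment.

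**Analysis.** In section III.2, "the primary outcome is the change in TSLP gene expression in epithelial cells after 2 weeks of treatment of inhaled corticosteroid compared to no treatment". "The difference between two randomized groups will be compared using the two-group" t-test, or by a Wilcoxon test if the data are skewed. The power statement covers this comparison alone: "Group sample sizes of 15 and 15 achieve 80% power to detect a difference of 1.3SD", "with a significance level (alpha) of 0.01 using a two-sided two-sample" t-test. Section II, item 1 puts Phase II at 40 subjects, not 30.

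**Purpose.** Specific Aim 3 states its hypothesis for asthmatics of both kinds together, then justifies it by phenotype: "The importance of this hypothesis in the characterization of irritant induced and allergic asthma" is said to lie in learning which markers are steroid sensitive or resistant. The section on anticipated results says the work could "help target specific interventions for asthma of different phenotypes as we proposed in phase II of the study".

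**What is absent.** For Phase II the plan gives no IA:AA quota, stratification, phenotype factor, within-phenotype estimate or phenotype-by-treatment estimate. The section on anticipated results does plan comparisons between the two types of asthma, but of sputum markers and miRNA. It does not mention the response to steroid.

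**The concern.** The purpose mentions phenotype and the analysis does not. Two consequences follow.

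- **Averaging.** If steroid lowered TSLP in one phenotype and not in the other, the pooled contrast would average responders with non-responders. A null result could not then be told apart from no response in either phenotype. Aim 3 wants to sort markers into steroid sensitive and steroid resistant, so a reader could misread such a null.
- **Precision.** If the phenotypes differ in mean change, whatever the treatment, that difference goes into the error term. Chance imbalance of IA and AA between small arms adds to it.

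Both can be eased at little cost, because each participant enters as IA or AA. This is so whether Phase II takes only Phase I completers (section III.1) or also new IA subjects (section II, item 5); those two statements need reconciling.

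**Working it through.** **Inputs from the plan:** 15 per arm, difference 1.3 SD, two-sided alpha 0.01, two-sample t-test (III.2); 40 subjects, taken as 20 per arm (II, item 1). **Assumptions of this review:** even IA:AA split unless noted, within-phenotype SD 1.

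**1. The plan's own figure.** Noncentrality = 1.3/√(2/15) = 1.3/0.365 = 3.56 on 28 df. The exact noncentral t gives 78.0% power. The difference detectable at exactly 80% is 1.33 SD, which rounds to 1.3, so the stated 80% is reproduced within rounding. At 20 per arm, power is 91%.

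**2. Effect in one phenotype only.** With 7 or 8 of 15 treated patients responding, the mean shift is 1.3 × 7/15 = 0.61 SD or 1.3 × 8/15 = 0.69 SD. Putting only that shift into the noncentral t gives 16% and 22%. That is too high, because mixing responders with non-responders raises the variance in the treated arm by about 0.25 × 1.3² = 0.42. Simulating the planned test (100,000 trials for t, 5,000 for Wilcoxon; phenotypes balanced across arms; no phenotype difference in the untreated) gives:

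| Responders among treated | t-test | Wilcoxon |
|---|---|---|
| 7 of 15 | 10% | 7% |
| 8 of 15 | 15% | 11% |
| 10 of 20 | 19% | 17% |

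The split matters. For the t-test, a responding phenotype making up about one third of the pool gives 4% at 15 per arm and 8% at 20. About two thirds gives 28% and 40%, and 80% gives 47% and 65%. At alpha 0.05 with an even split, power is 29-37% at 15 per arm and 44% at 20.

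**3. Precision.** Suppose mean change differs by 1 SD between phenotypes and steroid works equally in both. An even split adds 0.5 × 0.5 × 1² = 0.25 to the variance, so the SD becomes √1.25 = 1.12 and the standardised effect 1.3/1.12 = 1.16. Simulated power at 15 per arm:

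| Design | Power |
|---|---|
| Unstratified, unadjusted (as planned) | about 66% |
| Unstratified, phenotype as a factor | about 76% |
| Stratified, phenotype as a factor | about 78% |

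Most of the gain (76 − 66 = 10 of 78 − 66 = 12 points) comes from the factor. If phenotype does not affect change, the factor costs at most about 2 points.

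**4. Chance imbalance.** With 15 IA and 15 AA allocated 15:15 without stratification, the hypergeometric distribution gives a 47% chance of a 9:6 split or worse in an arm, and 14% for 10:5 or worse. At 10:5, a 1 SD phenotype difference moves that trial's contrast by (10/15 − 5/15) × 1 = 0.33 SD, in either direction with equal chance. This error is already part of the 66% in step 3.

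**5. What by-phenotype estimates can deliver.** Within one phenotype, power for 1.3 SD at alpha 0.01 is 32-39% with 7-8 per arm and 53% with 10. The difference between the IA and AA effects has SE = √(8/n): 0.73 SD at 15 per arm and 0.63 SD at 20. Power for a 1.3 SD difference is 18% and 27%. About 58 per arm would be needed for 80%.

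**The case against.** The strongest reply is that the planned test matches the hypothesis. Aim 3 is stated for IA and AA together, the TSLP hypothesis is pooled, and the rationale in the Aim 3 design text is to classify markers, not phenotypes. The targeting sentence is hedged and sits in a passage on the value of the programme. All of this stands, so the pooled comparison should stay primary. The gap is with the wider purpose, which the documents nonetheless state.

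Several stronger readings are tempting, and the documents do not support them:

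- *The study's own hypothesis predicts a different steroid response in IA and AA.* It does not. It posits similar inflammation arising from divergent miRNA pathways, and nothing predicts a phenotype-specific TSLP response. The one-phenotype effect is a scenario.
- *Unstratified assignment biases the result.* It does not. The shift in step 4 averages to zero over randomisations, and in simulation the type I error stayed at about 0.01. The 1 SD phenotype difference in change is also assumed; because the outcome is a change, differences in TSLP level may largely cancel.
- *The plan would declare TSLP steroid resistant after a null.* It has no such rule. The risk is one of interpretation.
- *Assignment is known to ignore phenotype.* This is inferred from silence. No method of randomisation is described at all.

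It is also fair to say that the remedy does not make Phase II able to settle the phenotype question, as step 5 shows.

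**Conclusion.** The concern holds in a limited form. As written, Phase II tests a pooled steroid effect, in line with its formal hypothesis, and yields no information on steroid response in IA or AA separately, although Aim 3 and the section on anticipated results give that wider purpose.

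A 1.3 SD effect confined to one phenotype would have about 10-15% power at 15 per arm (78% if both respond) or 19% at 20 per arm (91% if both respond). These figures assume an even split, SD 1, alpha 0.01 and no effect in the other phenotype. A reader might infer that such an effect would be missed whatever the mix. That goes too far: if the responding phenotype made up 80% of 20 per arm, power would be about 65%.

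Separately, if mean change differed by 1 SD between phenotypes, leaving phenotype out of design and analysis would cost about 12 points of power (66% against 78%). The change is worth making because it is nearly free, not because the primary analysis is invalid.

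**What to change.** - **Section III.1, Phase II:** state that assignment is stratified by phenotype (IA, AA). If assignment has already begun without stratification, make the analysis change only.
- **Section III.2, primary analysis:** keep Treatment versus No treatment over both phenotypes as primary, with phenotype as a factor in the model, or a stratified Wilcoxon test if the data are skewed.
- **Section III.2, exploratory analysis:** report the treatment effect in IA, the effect in AA and their difference, each with a confidence interval and labelled exploratory. State the number of IA and AA participants in each arm.
- **Interpretation:** state that a null pooled result will not be read as evidence of steroid resistance in either phenotype.
- **Related text:** reconcile the 40 Phase II subjects with the 15 + 15 of the power statement, and the two statements on whether new subjects may enter Phase II.

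The cost is two allocation lists, a few sentences and one degree of freedom, with no added participants or procedures. The by-phenotype estimates will be imprecise (power for the IA-AA difference about 18-27%), and the report should say so.
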